### Severity of Event

All AEs will be assessed by the qualified site investigator and the following guidelines will be used to describe severity.

- Mild** – Events require minimal or no treatment and do not interfere with the participant’s daily activities.
- Moderate** – Events result in a low level of inconvenience or concern. Moderate events may cause some interference with functioning.
- Severe** – Events interrupt a participant’s usual daily activity and may require systemic drug therapy or other treatment. Severe events are usually potentially life-threatening or incapacitating.

### Relationship to Study INTERVENTION

All AEs will have their relationship to study intervention assessed by the Qualified Site Investigator who examines and evaluates the participant based on temporal relationship and

his/her clinical judgment. The degree of certainty about causality will be graded using the categories below.

**-Definitely Related** – There is clear evidence to suggest a causal relationship, and other possible contributing factors can be ruled out. The clinical event occurs in a plausible time relationship to study intervention administration and cannot be explained for example, by concurrent disease or other drugs or chemicals.

**-Probably Related** – There is evidence to suggest a causal relationship, and the influence of other factors is unlikely. The clinical event occurs within a reasonable time after administration of the study intervention, is unlikely to be attributed for example to concurrent disease or other drugs or chemicals.

**-Potentially Related** – There is some evidence to suggest a causal relationship (e.g., the event occurred within a reasonable time after administration of the trial medication). However, other factors may have contributed to the event (e.g., the participant's clinical condition, other concomitant events). Although an AE may rate only as "possibly related" soon after discovery, it can be flagged as requiring more information and later be upgraded to "probably related" or "definitely related", as appropriate.

**-Unlikely to be related** – A clinical event whose temporal relationship to study intervention administration makes a causal relationship improbable (e.g., the event did not occur within a reasonable time after administration of the study intervention) and in which other drugs or chemicals or underlying disease provides plausible explanations (e.g., the participant's clinical condition, other concomitant treatments).

**-Not Related** – The AE is completely independent of study intervention administration, and evidence exists that the event is definitely related to another etiology. There must be an alternative, definitive etiology documented by the clinician.

#### Expectedness

The Qualified Site Investigator will be responsible for determining whether an AE/ADR is expected or unexpected. An AE/ADR will be considered unexpected if the nature, severity, or frequency of the event is not consistent with the risk information previously described for the study intervention. An unexpected ADR reaction will be defined explicitly as: an adverse reaction, the nature or severity of which is not consistent with the applicable product information.

#### Time Period and Frequency for Event Assessment and Follow-Up

AEs will be collected from the time the participant is consented until the participant has completed the study. The occurrence of an AE or SAE may come to the attention of study personnel during the ED enrolment visit, during the ED chart review, by a participant's caregiver contacting the study team, or finally by review by a study monitor. SAEs that could be related to dexamethasone (Appendix A) will be specifically solicited from participants' parents/caregivers on revisits. Participants will be followed for 30 days from the date of enrolment for adverse events.

All AEs will be captured on the follow-up CRF in REDCap. Information to be collected includes

an event description, date of onset, clinician's assessment of severity, relationship to study product (assessed by the qualified site investigator), and date of resolution/stabilization of the event and event outcome (resolved/recovered, recovered with sequelae, not recovered/not resolved, death and unknown). All AEs will be followed to adequate resolution or until the Qualified Site Investigator deems the event to be chronic or the participant has been deemed clinically stable.

### Adverse Event Reporting

MOP has been developed to ensure that all AEs are reported in a timely manner. The MOP will describe staff responsibility for completing and signing off on the AE reports, who will receive notification of AEs, and who is responsible for meeting site REB and regulatory requirements. AEs will be tabulated and reported to the DSMB and UoM HREB. Expected SAEs/SADR and unexpected SAE/SADR will be reported.

#### Croup disease-related events:

Disease related events that are not concluded to be related to the study drug by the Site Qualified Investigator and are part of the natural history of croup will not be reported as AEs (although they will be captured as part of study data collection):

- Hospitalization related to croup.
- The use of IV or NG rehydration for maintaining fluid balance related to croup.
- Cough, difficult breathing.
- Apnea.
- Intensive care admission related to croup; and
- Use of respiratory supports (such as supplemental oxygen, high flow nasal cannula, CPAP, and intubation/mechanical ventilation) in the treatment of croup.

#### **Pre-existing medical conditions:**

The deterioration, worsening or increase in frequency of a participant's pre-existing condition at any time during the study will be considered an AE.

#### **Laboratory Results:**

Laboratory results that are deemed clinically significant, as per the QI will be reported as an AE. For positive urine and blood cultures, we will utilize the following process. Urine and blood cultures that are more than 12 hours after time of patient enrollment and are positive should also be reported as an AE.

### Serious Adverse Event Reporting

The Qualified Site Investigator will report any SAE, whether or not considered study intervention related, and any SADR to the Sponsor-Investigator within 72 hours of becoming

aware of the event. The Qualified Site Investigator will complete a “Serious Adverse Event/Drug Reaction Report Form”. The Qualified Site Investigator will include an assessment of whether there is a reasonable possibility that the study intervention caused the event and whether the treatment was given, withheld, discontinued. Any additional requested information from the DSMB or Sponsor-Investigator should be completed as soon as possible. The site will report SAE/SADRs to UoM REB in accordance with the SAE/SADR reporting requirements. The Sponsor-Investigator will also inform the DSMB of the information provided from the site as soon as possible but no later than 7 days after the initial reporting.

If the SAE or SADR are also **unexpected**, the Sponsor- investigator will also file a Serious Unexpected ADR report with Health Canada:

- where the AE/ADR is neither fatal nor life-threatening, within 15 days after becoming aware of the information.
- where the AE/ADR is fatal or life-threatening, immediately where possible and, in any event, within 7 days after becoming aware of the information; and
- within 8 days after having informed Health Canada of the SAE/SADR, submit as complete as possible, a report which includes an assessment of the importance and implication of any findings.

In addition, the Sponsor-Investigator will notify the Site Investigator of SAE and SADR that are also **unexpected**:

- where the AE/ADR is neither fatal nor life-threatening, within 15 days after becoming aware of the information; and
- where the AE/ADR is fatal or life-threatening, immediately where possible and, in any event, within 7 days after becoming aware of the information.

### Reporting Events to Participants

All caregivers of the study participants will be informed in a timely manner if information becomes available that may be relevant to the study participant’s willingness to continue participation in the study.

Events of Special Interest: Not applicable.

Reporting of Pregnancy: Not applicable.

### Unanticipated Problems

#### Definition of Unanticipated Problems

**An Unanticipated problem (UP)** is any incident, experience, or outcome that meets all of the following criteria:

- Unexpected regarding nature, severity, or frequency given (a) the research procedures that are described in the protocol-related documents, such as the REB-approved research protocol and informed consent document; and (b) the characteristics of the participant population being studied;

- Related or possibly related to participation in the research (“possibly related” means there is a reasonable possibility that the incident, experience, or outcome may have been caused by the procedures involved in the research); and
- Suggests that the research places participants or others at a greater risk of harm (including physical, psychological, economic, or social harm) than was previously known or recognized.

### Unanticipated Problem Reporting

The qualified site investigator will report UPs to the Sponsor- Investigator, the UoM HREB according to their reporting policies. The UP report will include the following information:

- Protocol identifying information: protocol title and number, Qualified Site Investigator’s name, and the responsible HREB project/reference or case number.
- A detailed description of the event, incident, experience, or outcome.
- An explanation of the basis for determining that the event, incident, experience, or outcome represent a UP; and
- A description of any changes to the protocol or other corrective actions that have been taken or are proposed in response to the UP.

To satisfy the requirement for prompt reporting, UPs will be reported using the following timeline:

- UPs that are SAEs or SADRs will be reported to the Sponsor-Investigator, UoM REB, and DSMB according to the protocol.
- Any other UP will be reported to the Sponsor-Investigator within 15 days of the Qualified Site Investigator becoming aware of the problem and to the UoM HREB in accordance with their reporting guidelines; and
- All UPs will be reported to appropriate institutional officials (as required by an institution’s written reporting procedures).

### Reporting Unanticipated Problems to Participants

All caregivers of the study participants will be notified if at any time there are new UPs which may potentially impact willingness to continue participation in the study.

### Data management and statistical analysis plan

We will use Beta distributions to represent the individual priors for the probabilities elicited based on the mode and 95% credible interval. The aggregate prior distribution from the individual level distributions will be found using the equal-weighted linear pooling method to reduce biases introduced by overoptimism and overconfidence (43, 44). For definitive RCT, we will determine the total required sample size using the Average Length (AL) criterion - a method for Bayesian sample size calculation (45). Based on that sample size, we will simulate the type I error and power to evaluate the efficiency of the definitive RCT.

We will present the number of responses and the percentage of patients who would prefer the use dexamethasone at 0.15mg/kg versus 0.6mg/kg. We will also present the reasons for their choice.

## **IMPACT/SIGNIFICANCE:**

Implementing a vanguard RCT will help identify the potential challenges that may arise during a definitive RCT and, more importantly, an insight into how to mitigate the challenges. The success of this vanguard trial **will positively impact on cost and time needed for the definitive RCT**. Parental input in shared health decision-making is needed for quality health care. Locally, the Manitoba Quality and Learning framework (46) identifies patient experience and population health as two crucial aims.

## **EXPECTED OUTCOMES**

Implementing remote, real-time expert elicitation will generate reliable and robust sample size estimation and reliable noninferiority margin. We expect differences in the priority of study outcomes between the investigators and patients with lived experience. We expect that this will provide the groundwork for a robust and comprehensive definitive RCT in Canada to determine whether 0.15mg/kg is noninferior to 0.6mg/kg to treat croup.

## **STRENGTHS AND LIMITATIONS:**

**This is the first RCT to implement the Bayesian elicitation process simultaneously with patient engagement to assess the noninferiority of dexamethasone at 0.15mg/kg versus 0.6mg/kg to treat croup.** This is a vanguard RCT, which will provide a platform and experience for designing and implementing a definitive RCT. Our team has shown that remote, real-time expert elicitation is easy and cost-effective (35). Patient recruitment may be a challenge, but this can be addressed using our strong links to clinical trialists and our dedicated clinicians in Manitoba and Pediatric Emergency Research Canada (PERC).

## **KNOWLEDGE TRANSLATION (KT) AND MOBILIZATION PLAN**

### Existing KT platform:

We will disseminate the findings through the Translating Emergency Knowledge for Kids (TREKK) network, social media, newsletters, and national meetings. TREKK was created in 2011 as a national knowledge mobilization network through the Government of Canada's Networks of Centres of Excellence program to accelerate the speed at which the latest evidence in pediatric emergency care is put into practice (47). It has become a world leader in co-creating user-informed, high quality, evidence-based, impactful resources, including clinical tools (e.g., management algorithms, order sets, checklists), innovative parent tools (e.g., videos, ebooks, infographics) and 1–2-page summaries that share key issues and current, available evidence for managing acute pediatric illness (**>65,000 downloads from trekk.ca**) (48).

### Integrated KT plan:

I have an established connection with TREKK. This network will help facilitate receiving feedback on the findings from the chart review and vanguard RCT. I also have an established

connection with the patient engagement team through whom I will receive feedback from the rest of the patient partners. The synergy between feedback received from health care providers and patient partners will ensure a shared model input in the definitive RCT. There will be presentations at provincial, national (PERC), and international conferences. Any feedback on this vanguard trial will be considered in designing and implementing the definitive RCT.

## **GENDER AND SEX-BASED ANALYSIS**

There is a sex difference in croup occurring more in boys versus girls (49). The biological explanation for this is vague. We plan to investigate the sex difference in our population in a logistic regression model. In order to perform more sophisticated sex and gender analysis, we are collecting sex of patients in each treatment arm (**Figure 1**). Because evidence also supports gender difference in ED attendance (50), we will test the effect of interaction between sex and gender on return visits or readmission due to either dose of dexamethasone in regression models.

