### Inclusion criteria:

These are:

- Children aged **(6 months-5 years)** with clinical diagnosis of croup (1, 32).
- Presenting to the Winnipeg Children's Hospital ED

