### Vanguard RCT recruitment process and sample size estimation:

Based on the budget allocated for patient recruitment (**see attached budget**), sampling of children with clinical diagnosis of croup who presented to the WCH ED between January 2021 and January 2022 (**n=710**), and our experience from a similar trial that used 720 children (34), we plan to recruit 50 children within a year for this vanguard trial (Figure 1). **We will enrol 50% (25 children, in ratio 60:40% male to female) per treatment arm and assess for missing data and protocol adherence.** We will leverage a Bayesian elicitation process used by our team for an ongoing trial on bronchiolitis (35). We will elicit the probability of return visits or readmissions to ED within 7 days for each dose of dexamethasone at 0.15mg/kg versus 0.6mg/kg. The probabilities of revisits or readmissions to the ED closely reflect clinical decision making. We will then use bivariate elicitation to understand the relationship between the two probabilities (36, 37).

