## MEASURES TO MINIMIZE BIAS: RANDOMIZATION AND BLINDING

### Randomization

Computerized randomization will be performed by a statistician at the George and Fay Yee Centre for HealthCare Innovation to generate the randomization list. We will perform a computerized randomization in REDCap stratified by age (Figure 1). We will do a block randomization with random

blocks of undisclosed block sizes over the seasons to ensure that we get temporal distribution of croup cases. We will randomly assign patients into either the intervention or control in ratio 1:1. This process will help to reduce bias due to selection and residual confounding that may bias our results. Because croup season peaks over the fall and winter months in Canada, our randomization will consider this factor such that each arm will have an almost similar number per the peak season. While croup is common between 6 months and 5 years, a typical croup affects children between 6 months and 3 years. Based on this, we will randomize such that this age category (6 months-3years and >3 years – 5 years) has almost similar distribution in each arm.

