### Sequence Generation

A statistician (not otherwise involved in the study) at the George and Fay-Yee Centre for HealthCare Innovation will develop and maintain a computer-generated permuted-block randomization list, stratified by age. The randomization list will be sent to Pharmacy, where the list will be used to compound and label pre-packaged bottles numbered sequentially.

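### The planned logistic regression of the sex difference names no outcome: it cannot be fitted to croup occurrence, and on return visits a sex-by-dose model in 50 children will often have no finite estimate

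*Combined protocol and SAP*

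**What the plan says.** The section on gender and sex-based analysis begins with the observation that croup is commoner in boys and that the biological reason is unclear. It continues: "We plan to investigate the sex difference in our population in a logistic regression model". No dependent variable is given. It then says "we will test the effect of interaction between sex and gender on return visits or readmission due to either dose of dexamethasone", again by regression. Return visits or readmission is therefore the only regression outcome the section names, and the interaction it literally names is sex by gender. The section says that sex is being collected and mentions no gender variable.

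Three other places matter. The inclusion criteria admit children "with clinical diagnosis of croup". The recruitment and sample size section says "we plan to recruit 50 children within a year for this vanguard trial", with each arm described as "25 children, in ratio 60:40% male to female". Allocation is 1:1 from a "permuted-block randomization list, stratified by age", so sex is not a stratification factor. The statistical analysis section covers the elicited priors, their pooling, the sample size of the definitive trial and the reporting of preferences. It does not mention a sex model, sparse data or separation.

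**The concern.** The plan has to be workable on at least one reading of the missing outcome.

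If the outcome is having croup, it takes the same value in all 50 children and there is nothing to regress.

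If the outcome is return or readmission within 7 days, the data divide into four small cells by sex and dose. A cell with no returns makes the ordinary maximum-likelihood interaction infinite, and its Wald p-value then has no meaning.

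This is the only regression on trial data that the document describes. Followed as written, it would give no fit or, often, an unstable odds ratio by sex. The sex analysis is not one of the vanguard's stated feasibility objectives, so no decision about the definitive trial depends on it. What is at stake is a misleading secondary result.

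**Working it through.** **Inputs from the protocol.** 50 children, 1:1 allocation, 60:40 male to female within each arm, croup required for entry.

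**Input not in the protocol.** The 7-day return risk p. The recruitment and sample size section leaves it to elicitation, so p = 5%, 10%, 15% and 20% are assumptions.

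**Reproducing the plan's own figure.** 50 × 0.5 = 25 per arm. 25 × 0.6 = 15 boys and 25 × 0.4 = 10 girls. 2 × (15 + 10) = 50. The stated arm size agrees. The plan gives no event count, alpha or power for the sex analysis, so nothing else can be reproduced.

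**Reading 1: outcome is croup occurrence.** The inclusion criteria admit croup cases only. There are no non-cases, the outcome is constant and no logistic model exists. Taking the population to be the 710 children mentioned under recruitment does not help, because they too all had croup.

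**Reading 2: outcome is return or readmission, with a sex-by-dose interaction.** With cells of 15, 10, 15 and 10 and the same risk p in each,

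P(at least one cell with no return) = 1 − [1 − (1−p)^15]² × [1 − (1−p)^10]².

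At p = 10%: 0.9^15 = 0.2059 and 0.9^10 = 0.3487, so 1 − 0.7941² × 0.6513² = 1 − 0.6306 × 0.4242 = 0.73.

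| Assumed risk | Expected returns in 50 | P(empty sex-by-dose cell) |
|---|---|---|
| 5% | 2.5 | 95% |
| 10% | 5 | 73% |
| 15% | 7.5 | 46% |
| 20% | 10 | 26% |

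Solving for 50% gives p = 14.3%, or about 7 returns in 50.

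**Sensitivity at p = 10%.** Applying the ends of the interval for the relative risk of return in the rationale (0.71 and 1.17) to the low-dose arm gives 82% and 69%. Letting sex vary at random around 60%, instead of fixing it at 15 and 10, gives 75%.

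**Simpler models of return.** A sex-only model has no finite estimate when one sex has no returns: 1 − [1 − (1−p)^30] × [1 − (1−p)^20]. At p = 10% this is 1 − 0.9576 × 0.8784 = 16%; at p = 5% it is 1 − 0.7854 × 0.6415 = 50%. For an additive sex-plus-dose model, simulation (200,000 trials, each checked for separation) gives no finite estimate in 23% of trials at p = 10% and 61% at p = 5%.

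**Precision when a sex effect can be fitted.** For 30 boys against 20 girls, two-sided 5% level and normal approximation, power is 17% for 15% vs 5%, 14% for 20% vs 10%, and 37% for 30% vs 10%. These risk pairs are also assumptions.

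**The case against.** The strongest reply is that the empty-cell figures belong to a model the plan does not literally state. The text names sex by gender, not sex by dose, and sex by dose is an inference from the words "on return visits or readmission due to either dose of dexamethasone in regression models". That is fair. The figures apply only to that interaction, and the simpler models fail less often. The literal term offers no way out, however: the baseline data list includes sex and no gender item, so sex by gender cannot be estimated from what the text says is collected. The case report forms themselves are not reproduced.

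Second, the occurrence reading is not certain, since the sentence names no outcome. This also stands. What the text establishes is an unnamed outcome; croup occurrence is what the preceding sentences suggest.

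Third, a reader might infer that the regression cannot work at all. The documents do not support that. Only the occurrence reading is impossible. For returns, all four cells have events in 54% of trials at a 15% risk and 74% at 20% (100 minus 46 and 26), and a penalised or Bayesian fit gives an estimate even with an empty cell. Nor do the documents show that returns will be few, because no rate is stated.

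Fourth, a reader might take the 60:40 ratio as a further reason for failure. Consecutive enrolment and randomisation stratified by age alone suggest that it may be only an expected mix. Even a fixed ratio would do no harm to a model of returns, where sex is a covariate.

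Fifth, the plan does not specify maximum likelihood or Wald tests. True, but it says that it will test the interaction and names no alternative method, so the default fit is the reasonable assumption.

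**Conclusion.** The point holds in this form. The planned logistic regression lacks a named outcome. If the outcome is croup occurrence, it cannot be fitted to a sample made up only of croup cases; this follows from the text and needs no assumption. If it is return or readmission with a sex-by-dose interaction, ordinary maximum likelihood will often have no finite estimate, and more often than not only if the return risk is below about 14%. That conclusion rests on an assumed risk, equal risks across cells and about 15 boys and 10 girls per arm; the sensitivity checks at a 10% risk move the answer only between 69% and 82%. Simpler models of return can often be fitted once the risk reaches 10%, but they say little. The analysis is secondary, so this is a correction that should be made, not a threat to the trial.

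**What to change.** In the section on gender and sex-based analysis:

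- Name return visit or readmission within 7 days as the outcome, and replace the sex-by-gender term with sex by dose as the interaction of interest.
- For the vanguard, replace the regression test with a table of returns by sex and arm, with exact confidence intervals and no test.
- If a model is kept, fit it with a Firth-penalised or Bayesian likelihood and label it exploratory.
- Reserve the interaction test for the definitive trial.
- Describe the sex split of croup cases from the 710 earlier presentations or the screening records only if sex is recorded there. The protocol gives only the count for the former, and its stated re-check of sex covers enrolled participants.

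The cost is a change of wording, with no new participant data. The vanguard would yield no p-value for a sex interaction, which is a small loss given the power shown above.
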